13.1 Sample Size

In the ODYSSEY Long Term trial, the addition of alirocumab 150 mg to maximally tolerated statin therapy resulted in a reduction of LDL cholesterol of approximately 60% at 4 weeks⁵. Similar LDL reductions were seen even when used in statin-intolerant

patients, as demonstrated in the ODYSSEY Alternative trial²⁴. We anticipate that patients will have baseline LDL levels of approximately 124 mg/dL on first presentation², and that a >40% in LDL reduction will be observed after treatment with alirocumab + atorvastatin 80 mg on top of what is seen with placebo + atorvastatin 80 mg at 2 weeks (primary endpoint), with a standard deviation of approximately 25%. These estimates lead to a predicted power >99% ($\alpha=0.01$) with a sample size of 20 patients, and of >95% with a 25% loss to follow up at 14 days. We also expect that patients with an acute myocardial infarction to have increased CRP levels, peaking at 72 hours^{22,23}. A sample size of 20 patients will also provide a power of 65-85% to detect a reduction of 33-50% in CRP or IL-6 plasma levels at 72 hours or 14 days with alirocumab + atorvastatin 80 mg on top of placebo + atorvastatin 80 mg (secondary endpoint).

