Alirocumab in Patients with Acute Myocardial Infarction

A Randomized Controlled Double-Blinded Study

The VCU Alirocumab Response Trial

STUDY PROTOCOL

Principal Investigator: [name], PhD

Sponsor: Virginia Commonwealth University

Funding provided by: Regeneron Pharmaceuticals, Inc. and
Sanofi U.S.

TABLE OF CONTENTS

- 1) PERSONNEL**
- 2) PROTOCOL SUMMARY**
- 3) BACKGROUND INFORMATION AND SCIENTIFIC RATIONALE**
- 4) OBJECTIVES**
 - 4.1 Study objectives
 - 4.2 Study outcome measures
 - 4.3 Study endpoints
- 5) STUDY DESIGN**
- 6) ENROLLMENT IN THE STUDY**
 - 6.1 Inclusion criteria
 - 6.2 Exclusion criteria
- 7) RANDOMIZATION**
- 8) TREATMENT WITH THE INVESTIGATIONAL DRUG**
- 9) STUDY ASSESSMENT**
- 10) POTENTIAL BENEFITS AND RISKS**
 - 10.1 Alirocumab
 - 10.2 Social and psychological risks
 - 10.3 Testing Risks
 - 10.4 Direct benefits to study participants
- 11) ASSESSMENT OF SAFETY**
 - 11.1 Reporting of Adverse Events
- 12) DISCONTINUATION OF TREATMENT AND WITHDRAWAL**
- 13) STATISTICAL CONSIDERATIONS**
- 14) REFERENCES**

1) PERSONNEL

Name	Role	Institution/ Division
[name], PhD	Principal Investigator	VCU, Cardiology
[name]	Regulatory Coordinator	VCU, Cardiology
[name]	Investigator	VCU, Cardiology
[name] [name]	Investigator	VCU, School of Pharmacy
[name], MS	Investigator	VCU, Cardiology
[name]	Investigator	VCU, School of Pharmacy
[name], MS	Investigator	VCU, Cardiology
[name]	Investigator	VCU, Internal Medicine
[name]	Investigational Pharmacy	VCU, School of Pharmacy

2) PROTOCOL SUMMARY

- Title:** **Alirocumab in Patients with Acute Myocardial Infarction**
- Population:** 20 patients aged ≥ 21 years presenting with an acute spontaneous non-ST elevation myocardial infarction (NSTEMI) who are already taking at least moderate intensity statin therapy at time of hospital admission
- Description:** Phase IV clinical trial of the alirocumab, an inhibitor of the proprotein convertase subtilisin/kexin (PCSK9), or placebo added to high-intensity statin (atorvastatin 80 mg) in LDL cholesterol lowering during NSTEMI.
- Objectives:** To determine the effectiveness of alirocumab in further lowering cholesterol LDL and inflammatory biomarkers when initiated acutely in patients with NSTEMI, in addition to high intensity statin, atorvastatin 80 mg.
- Primary Endpoint:** Placebo-corrected percentage change in calculated LDL cholesterol from baseline to day 14.

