4.3 Study Endpoints

Primary Endpoint:

[figure not shown]
- Placebo-corrected percentage change in calculated LDL cholesterol from baseline to day 14.

Secondary Endpoints:

- Placebo-corrected percentage change in calculated LDL cholesterol from baseline to 72 hours;
- Placebo-corrected percentage change in PCSK9 levels from baseline to 72 hours and 14 days;
- Placebo-corrected percentage change in Lp(a) levels from baseline to 72 hours and 14 days;
- Placebo-corrected percentage change in inflammatory markers (hsCRP, IL-6, IL-10, and TNF- α) from baseline to 72 hours and 14 days;
- Safety and tolerability of alirocumab when initiated in the inpatient setting soon after an NSTEMI.

5) STUDY DESIGN

We designed an active-controlled, double-blinded study of alirocumab versus placebo in addition to high intensity statin, atorvastatin 80 mg, in patients who present with acute type I (spontaneous) NSTEMI and who are already taking a moderate-high intensity statin prior to admission.

The study is composed of two treatment arms exploring:

- a) Alirocumab 150 mg given as a single dose subcutaneously + Atorvastatin 80 mg orally daily;
- b) Matching placebo injection subcutaneously + Atorvastatin 80 mg daily.

6) ENROLLMENT IN THE STUDY

Patients who are admitted to the Pauley Heart Center in the VCU Medical Center will be screened for inclusion and exclusion criteria based on a cursory evaluation of the information available in their medical charts. This approach is supported by a partial waiver of informed consent for authorization to access protected health information to allow identification of the subjects. After identifying the potential subjects, the investigators will approach the subjects in a private manner and review the informed consent form approved by the Institutional Review Board. Any additional information about their medical history that is unclear or incomplete from the medical charts will be clarified by speaking with the patients and obtaining confirmatory outside medical records, with the consent of the patients, if deemed necessary.

Patients agreeing to participate in the study will sign the informed consent form and will be given a copy of the consent form signed by the investigator performing the informed consent process. No study procedures will occur prior to the subject signing the approved informed consent.

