13.2 Analysis of the data

Continuous variables will be reported as median and interquartile, because of potential deviation from Gaussian distribution. Discrete variables will be reported as N and %. For the primary endpoint, the comparison in the interval change in LDL cholesterol between alirocumab and placebo will be completed using an ANOVA for repeated measures and assessing the P value for time_x_group allocation. P values <0.05 will be considered significant. Missing data will not be input. For the purpose of safety analysis, all patients receiving the investigational drug will be considered, independent of missing data.

14) REFERENCES

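### Section 13.1 states primary-endpoint power at alpha 0.01, but Section 13.2 tests that endpoint at P<0.05, so the power of the test actually planned is stated nowhere

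*Combined protocol and SAP*

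**What the plan says.** The primary endpoint (Section 4.3) is "Placebo-corrected percentage change in calculated LDL cholesterol from baseline to day 14".

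Section 13.1 sizes the trial on that endpoint. It expects "a >40% in LDL reduction will be observed after treatment with alirocumab + atorvastatin 80 mg" beyond placebo at two weeks, "with a standard deviation of approximately 25" percent. From these inputs it reports a "predicted power >99% ($\alpha=0.01$) with a sample size of 20 patients", and power above 95% if a quarter of the patients are lost by day 14.

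Section 13.2 names the primary analysis: the comparison is made "using an ANOVA for repeated measures and assessing the P value for time_x_group allocation". The next sentence sets the threshold: "P values <0.05 will be considered significant".

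Neither section says whether the test is one-sided or two-sided. No other section reserves 0.01 for the primary endpoint, gives a multiplicity reason for it, or labels it a deliberately cautious planning value.

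**The concern.** The alpha in a power calculation is ordinarily the level at which the planned test will be run. Here the calculation uses 0.01 and the analysis uses 0.05, for the same endpoint and with no explanation.

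Two things are at stake. A reader of Section 13.1 will take the trial to be built around a 1% test, whereas a primary P of, say, 0.03 will be reported as significant under Section 13.2. And the reader is never told the power of the test that will be run, because the only figures given belong to another level.

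**Working it through.** **Inputs from the protocol.** Difference 40 percentage points, the floor of the >40% in Section 13.1. SD 25 points (13.1). 20 patients in total (Section 2), randomized 1:1 (Section 7), hence 10 per arm. Loss to follow-up 25%, leaving 15 evaluable (13.1). Attrition 10%, leaving 18 (Section 12). Levels 0.01 (13.1) and 0.05 (13.2).

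**Assumptions.** The test is two-sided. A two-sample comparison of percentage change stands in for the time-by-group test, because the protocol gives no within-patient correlation from which to compute the ANOVA. The 15 evaluable patients are split 8 and 7 for the t calculation and 7.5 per arm for the normal approximation.

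**Step 1: the plan's own figure.** The standard error of the difference is 25 × √(1/10 + 1/10) = 11.18, so the standardized effect is 40 / 11.18 = 3.578.

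- Normal approximation at 0.01: Φ(3.578 − 2.576) = Φ(1.002) = 84.2%.
- Noncentral t, 18 df, at 0.01: 74.8%.

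Neither reaches >99%. With 15 evaluable the figures are 69.9% and 54.9%, against >95%. Reading 20 as the number per arm does give both stated powers by the normal formula (99.4%, and 96.5% with 15 per arm), but Sections 2 and 7 give 20 in total. Whether that is the source of the figures cannot be told from the protocol.

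**Step 2: power at each level, difference 40, SD 25.**

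| Evaluable | 0.05, normal | 0.05, t | 0.01, normal | 0.01, t |
|---|---|---|---|---|
| 20 | 94.7% | 92.2% | 84.2% | 74.8% |
| 18 | 92.4% | 89.0% | 79.3% | 67.9% |
| 15 | 87.3% | 81.5% | 69.9% | 54.9% |

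Moving from 0.01 to 0.05 therefore does not rescue the stated powers at these inputs. One-sided testing at 0.05 gives 97.3% (normal) or 96.4% (t) with 20 patients, still short of 99%.

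**Step 3: observed difference needed.** Critical difference = t(1 − α/2, df) × SE.

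- 10 per arm, 18 df: 2.101 × 11.18 = 23.5 points at 0.05; 2.878 × 11.18 = 32.2 points at 0.01.
- 8 and 7, 13 df, SE = 25 × √(1/8 + 1/7) = 12.94: 27.95 points at 0.05; 38.98 points at 0.01.

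**Step 4: chance that P lies between the two levels.** This is power at 0.05 minus power at 0.01.

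| True difference | Evaluable | Method | Chance |
|---|---|---|---|
| 40 | 20 | t | 92.2 − 74.8 = 17.4% |
| 40 | 20 | normal | 94.7 − 84.2 = 10.5% |
| 45 | 20 | t | 96.7 − 85.8 = 10.9% |
| 50 | 20 | t | 98.8 − 93.0 = about 6% |
| 60 | 20 | t | 99.9 − 98.9 = about 1% |
| 40 | 18 | t | 89.0 − 67.9 = 21.1% |
| 40 | 15 | t | 81.5 − 54.9 = about 27% |

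With no true difference the chance is 5% − 1% = 4%.

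**The case against.** The strongest reply is that the protocol contains only one decision rule. Section 13.2 names the primary test and then gives 0.05, whereas the 0.01 in Section 13.1 is a parenthetical input to a power calculation. Nothing says that the endpoint fails if P exceeds 0.01. That stands. It also disposes of two stronger conclusions that a reader might draw:

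- A reader might infer that the success threshold is left open, to be picked once the P value is known. The text does not support this. Section 13.2 fixes 0.05 in advance, and moving to 0.01 afterwards would only make success harder.
- A reader might infer that the false-positive risk is inflated. It is not. Testing at 0.05 carries a nominal 5% risk whatever alpha was used for sizing, and sizing at a stricter level than the test is, in itself, conservative for power.

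A second reply is that the effect may well exceed 40 points, since Section 13.1 treats 40 as a floor and cites about 60% at four weeks in an earlier trial. That also stands as a limit on size. At 60 points the two levels almost never disagree, and with 20 patients power at 0.01 is about 99% (99.7% normal, 98.9% t).

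What remains is that the power statement refers to a level the analysis does not use. Calling the 0.01 a cautious planning value would answer this, but the protocol does not do so.

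**Conclusion.** The point holds as an inconsistency between the sizing and analysis sections that should be corrected. The operative level is 0.05, and Section 13.1 reports power at another level.

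The chance of a primary P between the two levels should be read as a range. With 20 evaluable patients it runs from about 1% at a true difference of 60 points to about 17% at 40; with 15 evaluable it reaches about 27% at 40. These figures rest on SD 25, two-sided testing and the t-test substitute; the planned ANOVA could give different values.

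Changing the alpha alone would not make Section 13.1 right. At its stated floor of 40 points and SD 25, 10 per arm does not give >99% at either level, nor >95% after a 25% loss.

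**What to change.** State in both Section 13.1 and Section 13.2 that the primary endpoint is tested at two-sided 0.05. In the same edit, replace >99% and >95% with the power at that level for a 40-point difference and SD 25: about 92% with 20 patients and 82% with 15 evaluable by t, or 95% and 87% by normal approximation, naming the method used. Simply deleting the 0.01 would leave both power claims standing without support.

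If the sponsor does intend a 1% test, Section 13.2 must say so, and Section 13.1 must then show about 75% power with 20 patients and 55% with 15 by t.

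The cost is a rewritten power sentence, a short addition on level and sidedness, and a less favourable stated power. The edit itself requires no change to visits, procedures or the number of patients.

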- Secondary Endpoints:** Placebo-corrected percentage change in calculated LDL cholesterol from baseline to 72 hours; placebo-corrected percentage change in PCSK9 levels from baseline to 72 hours and 14 days; placebo-corrected percentage change in lipoprotein(a) levels from baseline to 72 hours and 14 days; placebo-corrected percentage change in inflammatory markers (high-sensitivity CRP, IL-6, IL-10, and TNF- α) from baseline to 72 hours and 14 days; and safety and tolerability of alirocumab when initiated in the inpatient setting soon after an NSTEMI.
- Study Design:** Randomized, double-blinded, placebo-controlled phase IV clinical trial of a single dose of Alirocumab 150 mg or matched placebo in a 1:1 ratio. Patients will be assessed at enrollment, 72 hours and 14 days after treatment.

3) BACKGROUND INFORMATION AND SCIENTIFIC RATIONALE

Acute myocardial infarction (AMI) remains a leading cause of mortality and morbidity across the nation and worldwide. While major advances in reperfusion strategies over the past several decades have significantly reduced early mortality rates after AMI, patients who survive the index event are increasingly at risk for adverse cardiac remodeling and the sequelae of heart failure and sudden cardiac death¹. The aging population accelerates this problem, making heart failure a major public health concern. Heart failure, indeed, currently affects approximately five million Americans with increasing rates of prevalence and incidence.

Anticoagulants, antiplatelet agents, and neurohormonal blockers have become standard of care in the treatment of patients with AMI, given their established effects on mortality. Cholesterol-lowering drugs, primarily HMG-coA reductase inhibitors – statins – have been studied as a means not only to reduce LDL cholesterol (and hence the incidence of a first or recurrent AMI) but also as an adjunct to acute AMI therapy. In the MIRACL trial, atorvastatin 80mg was administered within 24 to 96 hours after presentation with acute coronary syndrome (ACS). When compared to placebo, the atorvastatin group had a reduction in the primary endpoint (composite of death, nonfatal AMI, cardiac arrest with resuscitation, or recurrent symptomatic myocardial infarction) from 17.4% to 14.8% (relative risk = 0.84 [0.70 – 1.00], p=0.048)².

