10.4 Potential benefits to study participants

The hypothesis being tested is that alirocumab will be well tolerated when initiated in the inpatient setting during an acute MI, and that it will be effective in further lowering LDL-C levels in addition to standard of care, possibly with the additional effect of attenuating the inflammatory response during acute myocardial infarction. There is no guarantee, however, that there is a benefit of using alirocumab in the setting of acute myocardial

infarction. There is however, also, no guarantee that the subject will receive alirocumab as 50% of subjects will receive placebo. Finally, we also cannot exclude the possibility, although highly unlikely, that alirocumab will provide harm in the investigated population. In the ODYSSEY Long-Term analysis, indeed, fewer patients experienced an acute myocardial infarction on alirocumab vs placebo (0.9% vs 2.3%, $P=0.01$), and there is no evidence suggesting that the patients who experienced an acute myocardial infarction while on alirocumab had a worse outcome than those on placebo, as shown by a trend toward reduced cardiac mortality with alirocumab (0.3% vs 0.9%)⁵.

11) ASSESSMENT OF SAFETY

Safety parameters will include data deriving from history and physical examination performed at each encounter, laboratory data, and results of functional and imaging tests obtained as part of standard clinical care. The patient will be encouraged to contact the research team at any time with any concern or change.

Disease-related data will be assessed including change in symptoms (or new symptoms), change in functional capacity, vital signs, and significant changes in medications.

Data specific to the treatment will also be assessed. The patient will be asked about symptoms. Changes to treatment for side-effects or unanticipated problems will be performed without breaking the randomization code, unless deemed necessary for the treatment of the individual patient by the physician caring for him, in which case the physician will be made aware while the remainder of the team, especially the investigators performing and interpreting the tests, will be maintained blinded, if possible.

The risks of the tests performed have been described above. In order to reduce risk, the procedures will be performed by skilled practitioners in the standard clinical fashion.

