- The sponsor shall be responsible for ensuring submission of required expedited and periodic reports to the appropriate Regulatory Authority (RA), the Ethics Committee and investigators of each country participating in the Investigator-Sponsored Study (ISS, based on applicable regulations).
- Any Periodic reports (e.g. Development Safety Update Report (DSUR)), submitted to Regulatory Authority must first be transmitted to Regeneron/Sanofi for review and comment
- The Sponsor must provide to Regeneron/Sanofi any New Safety Findings pertaining to safety of the Investigational product within one (1) business day (e.g. Data Safety Monitoring Board recommendations).

12) DISCONTINUATION OF STUDY PARTICIPATION AND WITHDRAWAL

Patients may withdraw from the study at any time. The patient can decide to forgo any study procedures that makes him/her uncomfortable or wish not to complete. The study doctor may however stop the participation of the patient in this study at any time for many reasons including (*but not limited to*) the study doctor thinks it is necessary for patient health or safety, the patient has not followed study instructions, or administrative reasons requiring withdrawal.

Loss to follow-up can occur due to patients' withdrawal or death. If patients are lost to follow up and their clinical condition cannot be established (alive vs dead, hospitalized vs not), they will be excluded from the initial analysis, and then reintroduced for sensitivity analysis considering all potential outcomes. A 10% attrition rate is a reasonable assumption.

13) STATISTICAL CONSIDERATIONS

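### Section 13.1 claims power above 99% (above 95% after 25% loss) at alpha 0.01, but its own inputs with 10 patients per arm give about 75% and 55% by t test

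*Combined protocol and SAP*

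**What the plan says.** Section 13.1 (Sample Size) expects LDL at two weeks to fall by more than 40% beyond the fall on placebo, "with a standard deviation of approximately 25"%. It continues: "These estimates lead to a predicted power >99"% at alpha 0.01 "with a sample size of 20 patients, and of >95% with a 25% loss to follow up at 14 days". It does not name the test, the sidedness, the number per arm or a within-patient correlation.

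Other sections fix the remaining inputs:

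- The Population entry of section 2 gives the trial size: "20 patients aged ≥ 21 years presenting" with NSTEMI.
- The Study Design entry of section 2 gives the allocation: "single dose of Alirocumab 150 mg or matched placebo in a 1:1 ratio". Section 10.4 agrees: "50% of subjects will receive placebo".
- Section 12 has a different loss figure from the 25% in section 13.1: "A 10% attrition rate is a reasonable assumption".
- Section 13.2 sets the level of the primary test, a repeated-measures ANOVA judged on its time-by-group term: "P values <0.05 will be considered significant".

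**The concern.** A difference of 40 with an SD of 25 is a standardized effect of 1.6. That is large, but with 10 patients per arm at alpha 0.01 it does not usually bring power above 99%, and a drop to 15 patients should cost much more than the few points the plan allows.

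This is the plan's only justification of N = 20 for the primary endpoint. A reader would take from it that a true 40-point effect would be missed less than 1% of the time, or less than 5% of the time after heavy loss. The power is also quoted at alpha 0.01 while the test is at 0.05, so even a correct figure would not describe the planned test directly.

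**Working it through.** **Inputs**

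- Difference in mean percentage change: 40 points, the floor of the stated range (section 13.1).
- SD: 25 points, read as the SD of percentage change (section 13.1).
- Patients: 20 in total at 1:1, so 10 v 10 (sections 2, 7 and 10.4). With 25% loss, 20 × 0.75 = 15, taken as 8 v 7. With 10% attrition, 20 × 0.90 = 18, so 9 v 9.
- Alpha: 0.01 (section 13.1) or 0.05 (section 13.2). Sidedness is not stated, so both were tried.

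**Formulas**

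- Standardized effect: d = 40/25 = 1.6.
- Noncentrality: ncp = d × √(n1·n2/(n1+n2)), with df = n1 + n2 − 2.
- Power by t test: P(T > t_crit), with T noncentral t(df, ncp). The opposite tail is negligible.
- Power by normal approximation: Φ(ncp − z_crit).

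**Trying to reproduce the stated figures, two-sided alpha 0.01**

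- 10 v 10: ncp = 1.6 × √5 = 3.578. With df = 18, t_crit = 2.878 and power is **74.8%**. Normal: Φ(3.578 − 2.576) = **84.2%**. Stated: above 99%.
- 8 v 7: ncp = 1.6 × √(56/15) = 3.091. With df = 13, t_crit = 3.012 and power is **54.9%**. Normal: Φ(3.091 − 2.576) = **69.7%**. Stated: above 95%.

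A simulation of 200,000 trials analysed by t test gave 74.7% and 55.0%.

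**More lenient choices, same effect and SD**

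| Test | 10 v 10: t (normal) | 8 v 7: t (normal) |
|---|---|---|
| Two-sided 0.01 | 74.8% (84.2%) | 54.9% (69.7%) |
| One-sided 0.01 | 83.6% (89.5%) | 67.0% (77.8%) |
| Two-sided 0.05 | 92.2% (94.7%) | 81.5% (87.1%) |
| One-sided 0.05 | 96.4% (97.3%) | 90.0% (92.6%) |

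No cell reaches its stated bound.

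**What would reach the bounds**

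- *Twenty per arm, falling to 15 per arm.* At two-sided 0.01 the normal approximation gives 99.4% and 96.5%, which meets both bounds; the t test gives 98.8% and 93.8%. A per-arm number may have been used as the total, but that is an inference.
- *A larger effect or smaller SD with 20 in total.* At two-sided 0.01 by t test, 99% at 10 v 10 needs d = 2.427 and 95% at 8 v 7 needs d = 2.520. Meeting both needs an effect of 25 × 2.520 = 63 points, or an SD of 40/2.520 = 15.9.

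**Power at the level of section 13.2 (two-sided 0.05, t test, 40-point effect)**

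| SD | 10 v 10 | 9 v 9 | 8 v 7 |
|---|---|---|---|
| 20 | 98.8% | 97.8% | 94.6% |
| 25 | 92.2% | 89.0% | 81.5% |
| 30 | 80.5% | 75.7% | 66.4% |

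At SD 25 the risk of missing a true 40-point effect is about 8% with complete data, 11% with 10% attrition and 18% with 25% loss.

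**The case against.** There are four serious points on the other side.

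1. *Forty is a floor.* The plan expects more than 40%, and has just cited about 60% at four weeks from an earlier trial. At two-sided 0.01, a 50-point effect gives 92.9% and 78.4% by t test. A 60-point effect gives 98.8% and 92.6% by t test, and 99.7% and 98.0% by normal approximation, so that last pair meets both bounds. This stands to the extent that the size of the gap must be tied to a 40-point effect. It does not rescue the claim: 40 is the only placebo-corrected value given, and a power stated for effects above a floor has to hold at the floor.

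2. *The SD is not defined, and the analysis is repeated-measures.* If 25 were the SD of single measurements, a within-patient correlation of 0.8 would give an SD of change of 25 × √(2 × 0.2) = 15.8, and power of 99.4% and 95.2% by t test. The plan states no correlation, however, and attaches the SD to the percentage reduction. The natural reading is the SD of percentage change.

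3. *The planned ANOVA might include all three time points.* LDL is also measured at day 3, and an interaction over three times has two degrees of freedom. The primary endpoint runs from baseline to day 14, and with those two times the time-by-group test is the same as a t test on the change. Section 13.2 would need to be read differently for this to matter.

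4. *Sizing at 0.01 and testing at 0.05 is conservative, and N need not change.* Both are true. The difference in alpha needs explaining and is not a second error. That the trial remains adequately powered at 0.05 limits the harm, but leaves the stated figures wrong.

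**Conclusion.** The concern holds. For a 40-point difference, an SD of percentage change of 25 and 20 patients at 1:1, the power claimed at alpha 0.01 is overstated by at least 99 − 74.8 = 24 points with complete data and 95 − 54.9 = 40 points after 25% loss, by two-sided t test. By normal approximation the excess is at least 15 and 25 points (99 − 84.2 = 14.8 and 95 − 69.7 = 25.3). No choice of sidedness, of 0.01 or 0.05, or of t or normal calculation brings these inputs to either stated bound. The readings that do (20 per arm, a 60-point effect by normal approximation, or a high within-patient correlation) each need an input that section 13.1 does not state.

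The sample-size statement must be corrected because it is wrong as written. The consequence for the trial is modest: at two-sided 0.05 the primary comparison keeps 92% power with complete data and 82% with 25% loss, if the SD is 25. With an SD of 30 and 25% loss it would be 66%.

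**What to change.** Keep N = 20 and restate section 13.1 at the level used in section 13.2, naming the test, sidedness, SD definition and number per arm. For example:

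> With 10 patients per arm, a 40-point difference between arms and an SD of percentage change in LDL cholesterol of 25 points, a two-sided two-sample t test at alpha 0.05 on the change from baseline to day 14 has 92% power. Power is 89% with 10% attrition (9 per arm) and 82% with 25% loss (15 patients).

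Add that, with baseline and day 14 as the two times, this t test on the change corresponds to the time-by-group test of section 13.2, so that the power statement and the analysis visibly match. If alpha 0.01 is kept for sizing, give 75% and 55% instead and say that the test itself is made at 0.05. If a larger effect, a smaller SD or a within-patient correlation was intended, state it with its basis and recompute.

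The cost is a text change in section 13.1 and a less favourable stated power. No extra patients are needed, and the design, the analysis in section 13.2 and the conduct of the trial are unchanged.
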